#### **6.1.14.2. Clinical Laboratory Evaluation**

The incidence rates of patients with treatment-emergent abnormal, high or low laboratory values at endpoint (LOCF) will be summarized for SP II, SP II and SP II/II, and compared between treatment groups for SP II. Listings of abnormal lab values and treatment-emergent abnormal lab values will also be presented.

A “treatment-emergent abnormal value at endpoint” is defined as a change from normal at all visits during baseline to abnormal at endpoint. A “treatment-emergent high value at endpoint” is defined as a change from a value less than or equal to the high limit at all visits during baseline to a value greater than the high limit at endpoint. A “treatment-emergent low value at endpoint” is defined as a change from a value greater than or equal to the low limit at all visits during baseline to a value less than the low limit at endpoint. High and low reference ranges for adolescent patients will be used to determine treatment emergent abnormal, high, low values. These reference ranges will be provided by a central laboratory. The same analysis will be done for “treatment-emergent abnormal value at anytime”, “treatment-emergent high value at any time”, and “treatment-emergent low value at any time”.

Treatment emergent liver function abnormalities at any time post-baseline for patients with normal ALT values (ALT <1 time upper limit normal) at last non-missing baseline will be summarized for SP II, SP III and SP II/III, and compared between treatment groups for SP II for the following categories:

ALT  $\geq$  3 times upper limit normal

ALT  $\geq$  5 times upper limit normal

ALT  $\geq$  10 times upper limit normal

Hy's Rule, ALT  $\geq$  3 times upper limit normal and total bilirubin  $\geq$  2 times upper limit normal.

A listing of patients with ALT  $\geq$  3 times upper limit normal at any time during post-baseline will be presented. And, a listing of all laboratory values will be presented.

For the continuous laboratory analytes, change from baseline to endpoint will be assessed using an ANOVA model (see Section 6.1.2 and 6.1.3) for Study Period II, and will be summarized for Study Period III and Study Period II/III. Rank transformed data for lab analytes will be used for the laboratory analysis. Within treatment testing of change from baseline will be based on a Wilcoxon Signed-Rank Test.

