**Table HMGW.6.1 Patient Population with Baseline and Post-baseline Definitions by Study Period and Type of Analysis**

Study Period / Analysis	Patient Population	Baseline Definition	Post-baseline Definition
Acute Phase			
Efficacy	Patients with a baseline and at least one post-baseline observation	Last of Visits 1-2	All Visits 3-8
TEAEs	All randomized patients	All Visits 1-2	All Visits 2.01-8
SAE and DCAE	All randomized patients	NA	All Visits 2.01-8
C-SSRS categorical analyses	All randomized patients	Lifetime baseline: All Visits 1-2 Lead-in baseline: Visit 2	All Visits 2.01-8
Treatment Emergent Abnormal Labs	Patients with normal laboratory values at all nonmissing baseline visits (with respect to direction being analyzed) and who have at least one post-baseline observation	All of Visits 1-2	All Visits 2.01-8
Treatment emergent low blood pressure	Patients with normal values at all nonmissing baseline visits (with respect to direction being analyzed) and who have at least one post-baseline observation. See Table HMGW.6.4 for normal limits of blood pressure.	Minimum value from Visits 1-2	All Visits 2.01-8
PCS in vital signs, weight, sustained blood pressure analyses	Vital signs: Patients with normal values at all nonmissing baseline visits (with respect to direction being analyzed) and who have at least one post-baseline observation. See Table HMGW.6.4 for normal limits of vital signs. Weight:	Low: Minimum value from Visits 1-2 High: Maximum value from Visits 1-2	All Visits 2.01-8

	Patients with non-missing baseline and at least one post-baseline value.		
Treatment-emergent changes in ECG intervals and heart rate	Patients with normal values at all nonmissing baseline visits (with respect to direction being analyzed) and who have at least one post-baseline observation. See Table HMGW.6.8 for normal limits of ECG.	Low: Minimum value from Visits 1-2 High: Maximum value from Visits 1-2	All Visits 2.01-8
Continuous Safety measures	Patients with a baseline and at least one post-baseline observation	Last of Visits 1-2	All Visits 3-8
Extension Phase			
Efficacy	Patients with a baseline and at least one post-baseline observation	Last of Visits 3-8	All Visits 9-15
TEAEs	All randomized patients entering extension phase	Maximum severity between $7 \leq \text{Visit} \leq 8$	All Visits 8.01-15
SAE and DCAE	All randomized patients entering extension phase	NA	All Visits 8.01-15

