C-SSRS categorical analyses	All randomized patients entering extension phase.	Lifetime baseline: All Visits 1-8 Lead-in baseline: $7 \leq \text{Visit} \leq 8$	All Visits 8.01-15
Treatment Emergent Abnormal Labs	Patients with normal laboratory values at all nonmissing baseline visits (with respect to direction being analyzed) and who have at least one post-baseline observation	All Visits 2.01-8	All Visits 8.01-15
Treatment emergent low blood pressure	Patients with normal values at all nonmissing baseline visits (with respect to direction being analyzed) and who have at least one post-baseline observation. See Table HMGW.6.4 for normal limits of blood pressure.	Minimum value from Visits 2.01-8	All Visits 8.01-15
PCS in vital signs, weight, sustained blood pressure analyses	Vital signs: Patients with normal values at all nonmissing baseline visits (with respect to direction being analyzed) and who have at least one post-baseline observation. See Table HMGW.6.4 for normal limits of vital signs. Weight: Patients with non-missing baseline and at least one post-baseline value.	Low: Minimum value from Visits 2.01-8 High: Maximum value from Visits 2.01-8	All Visits 8.01-15
Treatment-emergent changes in ECG intervals and heart rate	Patients with normal values at all nonmissing baseline visits (with	Low: Minimum value	All Visits 8.01-15

	respect to direction being analyzed) and who have at least one post-baseline observation. See Table HMGW.6.8 for normal limits of ECG.	from Visits 2.01–8 High: Maximum value from Visits 2.01–8	
Continuous Safety measures	Patients with a baseline and at least one post-baseline observation	Last of Visits 3-8 (for vital sign analysis, another baseline is: Last of Visits 1-2)	All Visits 9-15
Acute and Extension Phase Combined			
Efficacy	Patients with a baseline and at least one post-baseline observation	Last of Visits 1-2	All Visits 3-15
Treatment emergent low blood pressure	Patients with normal values at all nonmissing baseline visits (with respect to direction being analyzed) and who have at least one post-baseline observation. See Table HMGW.6.4 for normal limits of blood pressure.	Minimum value from Visits 1-2	All Visits 2.01-15

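### The ALT threshold and Hy's Rule incidence tables cover only patients with ALT below ULN at the last baseline, so a case arising from a mildly raised baseline is listed but not counted

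*SAP*

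**What the plan says.** Section 6.1.14.2 (Clinical Laboratory Evaluation) introduces the liver summary as treatment-emergent abnormalities at any time post-baseline, and restricts it to one population: "for patients with normal ALT values (ALT <1 time upper limit normal) at last non-missing baseline". Results "will be summarized for SP II, SP III and SP II/III, and compared between treatment groups for SP II for the following categories". Four categories follow under that single population: ALT ≥3×, ≥5× and ≥10× ULN, and Hy's Rule, defined as ALT at least "3 times upper limit normal and total bilirubin" at least 2 times ULN.

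The other categorical analysis that would count a raised ALT is the general treatment-emergent high count. It requires "a change from a value less than or equal to the high limit at all visits during baseline", and Table HMGW.6.1 describes its population as "Patients with normal laboratory values at all nonmissing baseline visits".

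Two outputs have no baseline restriction. One is a listing of patients with ALT at least "3 times upper limit normal at any time during post-baseline will be presented". For the other, "a listing of all laboratory values will be presented".

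**The concern.** The four categories are absolute multiples of ULN, chosen to pick out marked liver injury. Their meaning does not depend on whether the patient started just below or just above ULN: a rise from 1.2× to 3.5× ULN with bilirubin at 2.5× ULN meets Hy's Rule as the SAP defines it. Yet that patient is left out of the table because of the starting value, so the Hy's Rule row can show zero while a qualifying case sits in a listing.

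Elsewhere the SAP treats a severe absolute threshold differently. In Section 6.1.14.4, QTc above 500 msec is counted in every patient who was at or below 500 msec at baseline, so patients with QTc between the ordinary limit (450 or 470 msec) and 500 msec stay in. The potentially clinically significant weight analysis in Table HMGW.6.1 requires only a non-missing baseline. The SAP gives no reason for a stricter entry rule in the liver table.

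What is at stake is the completeness of the tabulated hepatic incidence, above all in the extension, where the baseline value used for exclusion is itself taken after randomization.

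**Working it through.** There is no stated figure to reproduce. The check follows patients through the rules.

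**1. Patient with raised pre-randomization ALT, SP II.** Take baseline ALT 1.2× ULN, then ALT 3.5× ULN with bilirubin 2.5× ULN.

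| Output (Section 6.1.14.2) | Entry rule | Patient included? |
|---|---|---|
| ALT ≥3×, ≥5×, ≥10× ULN | last baseline ALT <1× ULN | No (1.2 is not below 1) |
| Hy's Rule | same population | No |
| Treatment-emergent high ALT | ALT ≤ high limit at all baseline visits | No |
| Listing of ALT ≥3× ULN | none | Yes |
| Listing of all laboratory values | none | Yes |

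No planned laboratory incidence for ALT includes the patient, and the listings supply neither a denominator nor an arm comparison. The ALT listing is not described as flagging bilirubin or Hy's Rule.

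**2. SP III.** Table HMGW.6.1 gives two possible extension baselines: Visits 2.01–8 for treatment-emergent abnormal laboratory values, and the last of Visits 3–8 for continuous safety measures. Section 6.1.14.2 does not say which supplies the last non-missing value for the ALT categories. Both lie after randomization, so the conclusion is the same under either. Table HMGW.6.2 gives Visit 6 as the first scheduled post-baseline laboratory visit, so the value used will usually come from late in SP II.

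- *Randomized to duloxetine (DLX/DLX), ALT at or above ULN at the end of SP II:* out of the SP III table. The SP II/III table can recover the patient if the pre-treatment ALT was below ULN. This assumes that the combined period uses Visits 1–2 as baseline, as Table HMGW.6.1 does for continuous safety measures; it has no categorical laboratory row for that period.
- *Randomized to placebo (PLA/DLX), ALT at or above ULN at the end of SP II:* out of the SP III table. SP II/III cannot recover the patient, because Section 6.1.2 defines that group as patients randomized to duloxetine only. No threshold or Hy's Rule count on duloxetine includes this patient.

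**3. Possible size in SP II.** The SAP gives no share of patients with baseline ALT at or above ULN, so the shares below are assumptions. The sample size of 184 is from Section 5.2. Patients outside the table = 184 × share.

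| Assumed share | 184 × share | Patients (rounded) |
|---|---|---|
| 2% | 3.68 | 4 |
| 5% | 9.2 | 9 |
| 10% | 18.4 | 18 |
| 15% | 27.6 | 28 |

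These are patients outside the denominator, not missed events. The SAP gives no hepatic event rate from which to go further.

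**4. Definition of normal.** The ALT table requires a value strictly below ULN, while the treatment-emergent high rule accepts a value equal to the limit. A patient whose only baseline value is exactly at ULN is eligible for one table and not the other. The ALT table also looks at the last baseline value only, and the other rule at all baseline visits.

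**The case against.** The strongest reply is that this is a convention applied openly. The analysis is labelled treatment-emergent, and the SAP ties most such counts to a normal baseline (laboratory values, blood pressure, ECG intervals). The rule is clearly stated, and an all-patients count answers a different question. That stands as a reason not to call the rule an error. It does not explain why a severe threshold needs an entry limit at ULN, when the SAP's rule for QTc above 500 msec places the entry limit at the threshold itself.

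Three further objections stand, each against something a reader might infer:

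- *That Hy's Rule cases are lost.* They are not. Every such case has ALT ≥3× ULN by definition, so it must appear in the unrestricted listing. For very rare events, case review carries much of the information.
- *That the SP II arm comparison is biased.* It is not. The restriction uses a pre-randomization value applied alike to both arms, so the comparison remains randomized within a narrower group. SP II is also the only period in which arms are compared.
- *That a known, sizeable group is removed.* The document does not support this. It gives neither the share with raised ALT nor an expected number of hepatic events. Table HMGW.6.2 shows acute liver injury at baseline as an eligibility deviation, and any ALT entry limit would be in the protocol, which is not at hand. The group in SP II could be very small. An entry limit would not settle SP III, where the excluding value comes after randomization.

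The differences over what counts as normal are minor. Strict versus non-strict inequality affects only values exactly at ULN, and using the last value alone generally excludes fewer patients than requiring all visits to be normal.

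**Conclusion.** The point holds as a gap in tabulated safety reporting. As written, no planned laboratory incidence includes an ALT ≥3× ULN or Hy's Rule case in a patient whose last baseline ALT was above ULN; the case is visible only in listings. In SP II this narrows the population without biasing the comparison. In SP III it has more consequence: patients with ALT at or above ULN at the end of SP II leave the table, and for placebo/duloxetine patients no other table brings them back.

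The size is unknown. About 4 to 28 of 184 patients in SP II follows only from an assumed share of 2% to 15%. No efficacy conclusion depends on this table, and the listings preserve visibility of individual cases, so it is a worthwhile, inexpensive improvement and not a threat to the trial's validity.

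**What to change.** In Section 6.1.14.2, tabulate ALT ≥3×, ≥5× and ≥10× ULN for all patients with at least one post-baseline ALT, and Hy's Rule for all with post-baseline ALT and total bilirubin, whatever the baseline value, in SP II, SP III and SP II/III. Keep the normal-baseline table as supportive, define normal there as ALT ≤ ULN to match the treatment-emergent high rule, and state which baseline window it uses in each period.

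The cost is SAP wording and one extra table per period from data already collected. Conduct, sample size and significance level are unaffected. The drawback is that some elevations predating treatment will be counted; the supportive table separates them.

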### 6.1.14.3. Vital Signs and Other Physical Findings

In this study, the vital signs (blood pressure and pulse) are collected in triplicate at every visit, with readings at least 3 minutes apart. At each visit, the mean of this triplicate will be used as the blood pressure or pulse value for that visit. For categorical analysis, the lowest value during baseline (mean value of triplicates from each visit) will be used to determine treatment-emergent or potentially clinically significant low value; the highest value during baseline (mean value of triplicates from each visit) will be used to determine potentially clinically significant high values.

The incidence of patients with treatment-emergent low blood pressure at endpoint (LOCF) and at any time will be summarized for SP II, SP III, and SP II/III, and compared between treatment groups for SP II. Table HMGW.6.5 provides the criteria for treatment emergent low blood pressure for the relevant age categories. The baselines and post-baseline of blood pressure for Study Period II, Study Period III and Study Period II/III are as described in Table HMGW.6.1. Patients with low blood pressure at baseline will be excluded from the analysis, and only patients with normal baseline values with respect to the direction will be included in the analysis. The normal limits of vital signs at baseline are as described in Table HMGW.6.4.

**Table HMGW.6.4 Normal Limits of Vital Signs at Baseline**

Parameter	Age (Years)	Normal Limits for treatment emergent Low	Normal Limits for treatment emergent or PCS high
Pulse (bpm)	Adolescent (13-17)	$\geq$ 50	$\leq$ 120
Diastolic BP (mm Hg)	Adolescent (13-17)	$>$ 50	Value $\leq$ 95 th percentile (based on age, gender, and height)
Systolic BP (mm Hg)	Adolescent (13-17)	$>$ 90	Value $\leq$ 95 th percentile (based on age, gender, and height)

**Table HMGW.6.5 Criteria to Identify Patients with Treatment-Emergent Abnormalities in Vital Signs.**

Parameter	Age (Years)	Low Value	High Value
Diastolic BP (mm Hg)	Adolescent (13-17)	$\leq 50$ and decrease of $\geq 10$	NA
Systolic BP (mm Hg)	Adolescent (13-17)	$\leq 90$ and decrease of $\geq 20$	NA

**Table HMGW.6.6 Criteria to Identify Patients with Potentially Clinically Significant Abnormalities in Vital Signs.**

Parameter	Low Value	High Value
Pulse (bpm) Adolescents (13-17)	$<50$ and a decrease of $\geq 15$	$>120$ and increase of $\geq 15$
Weight	Decrease of at least 3.5% from baseline low value	N/A
Diastolic BP (mm Hg)	N/A	Value $> 95^{\text{th}}$ percentile* (based on age, gender, and height) AND Increase $\geq 5$ mm Hg from baseline
Systolic BP (mm Hg)	N/A	Value $> 95^{\text{th}}$ percentile* (based on age, gender, and height) AND Increase $\geq 5$ mm Hg from baseline

N/A = Not applicable

\*National High Blood Pressure Education Program Working Group. The fourth report on the diagnosis, evaluation, and treatment of high blood pressure in children and adolescents. *Pediatrics* 2004 August;114(2 Suppl 4th Report):555-76.

The incidence of patients meeting criteria for potentially clinically significant (PCS) values in vital signs and weight at endpoint (LOCF) and at any time will be summarized for SP II, SP III and SP II/III, and compared between treatment groups for SP II. Patients with abnormal vital signs at baseline with respect to direction being analyzed will be excluded from the analysis. Table HMGW 6.4 displays the normal limits of vital signs at baseline. In addition, the number of patients with abnormal blood pressure values at baseline will be summarized. Potentially

clinically significant changes in vital signs will be based on criteria shown in Table HMGW.6.6. To calculate the percentiles of blood pressure value for each age/gender/height percentile combination, the following steps will be followed:

1. Height percentiles for each age and gender combination will be calculated first based on the most recent CDC growth charts. The SAS code from CDC website (<http://www.cdc.gov/nccdphp/dnpao/growthcharts/resources/sas.htm>) will be utilized for the height percentile calculation.
  - a. First, L (power in the Box-Cox transformation), M (Mean) and S (Coefficient of variation) will be extracted from 2000 CDC growth charts for United States for height.
  - b. Z-score of height with corresponding age in months will be calculated using the following formula:

$$Z_{score} = \frac{\left(\frac{Height}{M}\right)^L - 1}{L * S}$$

- c. Percentile of height will be the probability that an observation from the standard normal distribution is less than or equal to Z-score.
2. The blood pressure percentile for each age, gender and height percentile combination will be calculated as follows (National Heart, Lung, and Blood Institute's National High Blood Pressure Education Program Working Group on High Blood Pressure in Children and Adolescents (2004)).
  - a. Compute the expected blood pressure values ( $\mu$ ) for kids of age  $y$  years and height Z-score ( $Z_{ht}$ ) given by

$$\mu = \alpha + \sum_{j=1}^4 \beta_j (y-10)^j + \sum_{k=1}^4 \gamma_k (Z_{ht})^k$$

Where  $\alpha, \beta_1, \dots, \beta_4$  and  $\gamma_1, \dots, \gamma_4$  are given in the 3rd column of appendix table B-1 of the fourth report of the diagnosis, evaluation and Treatment of High Blood Pressure in Children and Adolescents (2004).

- b. Z-score of blood pressure is given by :

$$Z_{bp} = \frac{(x - \mu)}{\sigma}$$

Where  $\sigma$  is given in the 3rd column of appendix table B-1 of the fourth report of the diagnosis, evaluation and Treatment of High Blood Pressure in Children and Adolescents (2004).

- c. Percentile of blood pressure will be the probability that an observation from the standard normal distribution is less than or equal to Z-score.

The incidence of patients with sustained elevated blood pressure will be summarized for SP II, SP III, and SP II/III, and compared between treatment groups for SP II. Blood pressure has sustained elevation if patient's blood pressure value meets PCS criteria at 3 consecutive post-baseline visits. PCS criteria are outlined at Table HMGW 6.6.

All vital signs data, patients with sustained blood pressure elevation, and patients with PCS vital signs will be presented in separate listings.

Change from baseline in vital signs (blood pressure and pulse), weight, and height data will be analyzed using an ANCOVA model with baseline values as covariates (see Sections 6.1.2 and 6.1.3). Raw values will be used for these analyses unless normality assumptions appear to be violated in which case the data will be rank transformed. These analyses will include summaries of baseline values, endpoint (LOCF) values, and change from baseline to endpoint (LOCF) by treatment group for SP II, SP III and SP II/III separately. Change from baseline in vital signs (blood pressure and pulse) and weight will also be summarized for SP IV. For SP IV, change from baseline in vital signs and weight data will be analyzed using a simple linear regression model with change from baseline as the response variable and the baseline value as the independent variable.

Change from baseline in vital signs (blood pressure and pulse) and weight will also be analyzed using an MMRM model (see Section 6.1.2) for SP II, SP III and SP II/III separately. Within treatment testing of change from baseline will be conducted.

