## 4. Study Objectives

### 4.1. Primary Objective

The primary objective of this study is to evaluate the efficacy of duloxetine 30/60 mg once daily (QD) compared with placebo on the reduction of average pain severity as measured by the Brief Pain Inventory (BPI) – Modified Short Form: Adolescent Version 24-hour average pain severity rating (for simplicity, it is referred to as the BPI average pain severity hereafter) during a 13-week, double-blind treatment phase in adolescents (aged 13 to 17 years) with Juvenile Primary Fibromyalgia Syndrome (JPFS), as defined by Yunus and Masi (Yunus and Masi 1985).

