### 5.1. Summary of Study Design

Study F1J-MC-HMGW (HMGW) is a Phase 3b, multicenter, randomized clinical trial of duloxetine versus placebo for the treatment of JPFS in adolescents. The study design includes 4 study periods. Following Study Period I (screening phase), eligible patients enter Study Period II, the acute 13-week parallel, randomized, double-blind, placebo-controlled treatment period of duloxetine 30/60 mg QD. Upon completion of the 13-week double-blind period, patients enter Study Period III, a 26-week, open-label extension phase of duloxetine 30/60 mg QD. A 1-week drug taper period (Study Period IV) is required for all patients who discontinue for any reason between Visit 4 to Visit 8 during Study Period II, or who complete/discontinue Study Period III on duloxetine 60 mg QD.

Figure HMGW.5.1 illustrates the study design.

Abbreviations: DB = double-blind; DLX = duloxetine; OL = open-label; QD = once-daily

a After Visit 3, patients increased to 60 mg duloxetine can have their dose decreased 1 time, at a scheduled or unscheduled Visit. Once 60 mg dose is decreased to 30 mg, it cannot be increased again during Study Period II.

b At Visits 4 through 8, patients randomized to placebo or DLX 30 mg who discontinue prior to entering the open-label extension treatment period (Study Period III) will receive placebo in the drug taper period.

c At Visits 9 through 14 in Study Period III, dose increases are permitted at scheduled visits (to a maximum dose of 60 mg QD) and dose decreases are permitted at scheduled or unscheduled visits (to a minimum dose of 30 mg QD).

d Patients who complete/discontinue Study Period III on DLX 30 mg do not need to enter the drug taper period.

**Figure HMGW.5.1** Illustration of study design for Protocol F1J-MC-HMGW.

Study Period I is a screening period of approximately 1 week in duration, but not more than 30 days, during which patients will be screened for study eligibility.

Study Period II is a 13-week, acute treatment period. During Study Period II, at Visit 2, patients who meet all study criteria for enrollment will be randomly assigned in a 1:1 ratio to duloxetine or placebo by a computer-generated random sequence using an interactive voice response system (IVRS). All patients will receive investigational product (IP) beginning at Visit 2 and will be instructed to start taking their IP the morning after Visit 2.

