Patients randomly assigned to placebo will remain on placebo throughout Study Period II.

Patients randomly assigned to the duloxetine treatment group will remain on duloxetine throughout Study Period II. Duloxetine patients will initially take a 30 mg QD dose of duloxetine for 1 week. Starting at Visit 3 through Visit 6, the dose can be increased from 30 mg QD to 60 mg QD. By Visit 4, comorbid MDD and/or GAD patients receiving a 30-mg QD dose should be increased to a 60-mg QD dose, unless the patient is experiencing significant intolerance to the 30-mg dose. Beginning at Visit 7, no dose increases can be made. Dose-escalation criteria for all patients is based on investigator's clinical judgment. Dose increase can only occur at scheduled study visits. If necessary due to intolerability, for those patients on a 60-mg QD dose, a one-time dose decrease to 30 mg may occur at a scheduled or unscheduled visit. Once the 60-mg dose is decreased to 30 mg, it cannot be increased again during Study Period II. If the patient has already had their 1 dose decrease, and at a subsequent time cannot tolerate the investigational product dose well enough to remain compliant, the patient should be discontinued.

Study Period III is a 26-week, open-label extension treatment phase. Patients randomized either to the duloxetine or placebo treatment group during Study Period II will enter Study Period III on a 30-mg dose of duloxetine for 1 week. The duloxetine dose may be increased to 60 mg QD only at a scheduled Visit starting at Visit 9 (Week 14). As in Study Period II, additional dose-escalation consideration should be given to all patients with comorbid MDD and/or GAD at study entry. At Visit 9, the comorbid MDD and/or GAD patients should have their 30-mg dose increased to 60 mg, unless the patient is experiencing significant intolerance to the 30-mg dose. From Visit 9 to Visit 14, dose modifications are allowed. Dose increases (up to 60 mg QD) are only permitted at scheduled visits. Dose decreases (down to 30 mg QD) are permitted at either scheduled or unscheduled visits. Dose adjustments are to be based on the investigator's clinical judgment of treatment response and tolerability at the patient's current dose.

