#### 6.1.2. General Considerations

Efficacy and safety analyses will be done on an intent-to-treat (ITT) basis unless otherwise specified. An intent-to-treat analysis is an analysis of data by the groups to which patients are assigned by random allocation, even if the patient does not take the assigned treatment, does not receive the correct treatment, or otherwise does not follow the protocol.

All efficacy and safety analyses of continuous measures will include randomized patients with both a baseline and at least one post-baseline value for the variable being analyzed. For efficacy and continuous safety variables, baseline is defined as the last measurement taken at, or prior to the visit where the study period begins; endpoint is defined as the last non-missing measurement for the study period of interest. Table HMGW 6.1 provides baseline and post-baseline definitions for all variables.

Statistical analyses will be carried out for Study Period II, III, and IV (SP II-IV). All tests of hypotheses will be evaluated based on a two-sided significance level of 0.05 unless otherwise specified. No adjustments for multiple comparisons will be made.

For SP II, a patient's treatment group will be determined by the treatment to which the patient is randomized: either duloxetine (DLX) or placebo (PLA).

For SP III, the following treatment groups will be determined by the randomized treatment at SP II and extension phase treatment at SP III:

PLA/DLX: patients who are randomized to placebo at SP II and who enter SP III and take duloxetine.

DLX/DLX: patients who are randomized to duloxetine at SP II and who enter SP III and take duloxetine.

No statistical comparisons will be conducted to compare the two treatment groups PLA/DLX and DLX/DLX during SP III unless otherwise noted. For continuous measures, when appropriate, within treatment testing of change from baseline for selected safety and efficacy measures will be conducted for SP III.

For SP II/III, one treatment group will be determined by the randomized treatment at SP II:

DLX: patients who are randomized to duloxetine at SPII, including patients who may have discontinued early at SPII or who enter SPIII.

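### In the uncontrolled extension, raw change in weight and height can mask slowed growth in 13 to 17 year olds; add age- and sex-standardised z-scores

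*SAP*

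**What the plan says.** The population is defined in section 4.1: "in adolescents (aged 13 to 17 years) with Juvenile Primary Fibromyalgia Syndrome (JPFS". Section 5.1 gives the lengths: "Study Period II is a 13-week, acute treatment period" and "Study Period III is a 26-week, open-label extension treatment phase". Both randomised groups "will enter Study Period III on a 30-mg dose of duloxetine for 1 week", so no patient is untreated in the extension.

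Section 6.1.2 plans no comparison of the two treatment sequences in Study Period III, and the models there drop the treatment term. It adds: "For SP II/III, one treatment group will be determined by the randomized treatment at SP II". That group is the patients randomised to duloxetine.

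Section 6.1.14.3 plans, for Study Periods II, III and II/III:

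- **ANCOVA:** "Change from baseline in vital signs (blood pressure and pulse), weight, and height data will be analyzed using an ANCOVA model with baseline values". Here the baseline is the covariate, and raw values are used, or ranks if normality fails.
- **Repeated measures:** vital signs and weight are also analysed by MMRM, and within-treatment testing of change is planned. Height is not named in that paragraph.
- **Categorical rule (Table HMGW.6.6):** for weight, "Decrease of at least 3.5% from baseline low value", assessed at endpoint and at any time. Height has no rule.

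The same section standardises height, but only as a step towards blood pressure percentiles: "Height percentiles for each age and gender combination will be calculated first based on the most recent CDC growth charts". The CDC weight-for-age file is in the reference list, but no analysis uses it.

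**The concern.** In growing patients, change from baseline is expected growth plus any drug effect. With a concurrent placebo arm, growth cancels in the contrast. Without one, a test of change against zero uses a null that does not fit a patient who should be gaining weight. The general ANCOVA and MMRM models have no age or sex term that would help.

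Section 4.2 makes extension safety a secondary objective, and section 6.1.14 names height and weight among the safety measures. The extension supplies the longest exposure in the trial. If slowed growth occurred there, the planned summaries could show a mean change near zero or a small gain, which reads as reassuring.

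**Working it through.** **1. Which periods have a control**

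| Period | Length | Control | Raw change reflects |
|---|---|---|---|
| II | 13 weeks | Randomised placebo | Growth cancels in the contrast |
| III | 26 weeks | None; all on duloxetine | Growth plus drug effect |
| II/III | 13 + 26 = 39 weeks | None; duloxetine group only | Growth plus drug effect |

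**2. Expected growth.** The SAP has no figure to reproduce. Assumed ranges, by age and sex: 1 to 5 kg per year and 0 to 6 cm per year. Expected gain = annual rate × weeks / 52.

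- 26 weeks (26/52 = 0.5 year): 0.5 to 2.5 kg; 0 to 3.0 cm.
- 39 weeks (39/52 = 0.75 year): 0.75 to 3.75 kg; 0 to 4.5 cm.

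A drug-related shortfall equal to these amounts would give a mean raw change of zero.

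**3. What the 3.5% rule sees.** Take a 50 kg patient (assumed), with the baseline low equal to baseline weight.

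- Flag: 0.035 × 50 = 1.75 kg lost.
- Expected weight at +4%: 52.00 kg. This is 2 kg over 39 weeks, or 2 / 0.75 = 2.67 kg per year, inside the assumed range.
- Observed weight at −0.5%: 49.75 kg.
- Shortfall: 52.00 − 49.75 = 2.25 kg, and 2.25 / 52.00 = 4.3% of expected weight.
- Observed loss: 0.25 kg, below 1.75 kg, so not flagged.

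**4. Shortfall needed to reach the flag at week 39.** For an assumed 55 kg patient the flag is 0.035 × 55 = 1.925 kg. Shortfall = (1.925 + expected gain) / (55 + expected gain).

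| Assumed gain per year | Expected gain, 39 weeks | Shortfall at flag | % of expected weight |
|---|---|---|---|
| 1 kg | 0.75 kg | 2.68 kg | 4.8% |
| 3 kg | 2.25 kg | 4.18 kg | 7.3% |
| 5 kg | 3.75 kg | 5.68 kg | 9.7% |

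So a rule set at 3.5% acts in the uncontrolled data as a rule of about 5% to 10% below expected weight.

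**5. The reference value in Study Period III.** Table HMGW.6.1 takes the baseline low for this period as the minimum over Visits 2.01 to 8. For patients already on duloxetine this is an on-treatment value, so weight lost in Study Period II lowers the reference. Study Period II/III uses Visits 1 to 2 and does not have this feature.

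**6. What is already available.** Section 6.1.14.3 writes out the LMS formula, Z = ((X/M)^L − 1)/(L × S), for height with age in months, and points to the CDC code. Table HMGW.6.2 counts missing height or weight at a scheduled visit as a significant deviation, so the data are expected at each visit.

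**The case against.** The best case for the plan has five parts.

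- **The randomised comparison answers the drug question for 13 weeks.** This stands. A reader might infer that raw change misleads throughout the 39 weeks. It does not: expected growth is the same in both arms of Study Period II, so that contrast is not biased by growth.
- **The SAP states no growth objective.** This also stands. Section 4.2 speaks only of extension safety, so a reader should not infer that a declared growth objective goes unanswered. Height and weight are nevertheless listed safety measures for that phase.
- **Other displays would show a problem.** The 3.5% rule applies at any time, so early loss can be caught. The MMRM shows the course by visit, adverse events are summarised, and data are listed. This stands for actual weight loss. It does not stand for slowed gain, which is not a fall; a flattening mean after week 13 has nothing to be compared with.
- **The size is assumed.** True. At the low end (0.75 kg, 0 cm) masking is slight, and older patients may have finished growing. Growth can hide an effect; the documents do not show that it will.
- **Z-scores do not supply a control.** True. A shift could reflect illness, activity or other treatment. They remove expected growth relative to a US reference population, and no more.

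**Conclusion.** The point holds for Study Period III and Study Period II/III. There, raw change in weight and height, and the test of weight change against zero, cannot distinguish normal growth from slowed growth, and the 3.5% rule does not fill the gap. The Study Period II comparison and the primary pain analysis are untouched.

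On assumed gains of 1 to 5 kg per year, the growth that could be offset unseen is 0.5 to 2.5 kg over 26 weeks and 0.75 to 3.75 kg over 39 weeks. These figures rest on growth rates and body weights that are not in the SAP.

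A reader might infer that standardised scores would then establish or exclude a drug effect on growth. The design does not support that: the extension has no concurrent control on any scale. The gain is in interpretability, not causal proof. This is a cheap improvement to the analysis; the planned analyses can be run as written.

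**What to change.** In section 6.1.14.3:

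- Add change from baseline in CDC age- and sex-specific z-scores for weight and height for Study Periods III and II/III, and for Study Period II for continuity. Use the LMS method already given, the weight-for-age file already cited, and age at each visit.
- State that extension weight and height will be interpreted mainly from these z-scores. Keep the raw summaries and the 3.5% rule unchanged.
- State that the z-scores remove expected growth relative to a US reference population, are not a concurrent control and do not establish causality.
- Reconcile section 6.1.14, which limits Study Period III safety to descriptive statistics, with section 6.1.14.3, which plans models and within-treatment tests there.

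The cost is a few sentences and tables. Height z-scores are already computed for blood pressure, and no new data are needed. The drawback is that any non-US patients are referred to US charts, which the blood pressure percentiles already accept for height.
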